2.3. Overall Survival (OS) after crossover to Next-line Ibrutinib for Crossover Subjects

OS after crossover to ibrutinib is defined from date of crossover to ibrutinib to the date of death due to any cause. Subjects who are alive or exited the study with unknown death status will be censored at the last date known to be alive. OS distribution is estimated by Kaplan-Meier method. Median OS and landmark estimates will be provided.

APPENDIX

Table 1 Summaries of Data and Statistical Methods

Parameters	Definitions and Statistical Methods
Demographics and baseline Characteristics	Information obtained at study start. Characteristics included age, gender, race, ethnicity, geographic region, weight, height, BSA, number of prior treatment lines, estimated creatinine clearance rate and other baseline characteristics.
Subject disposition	The number of subjects continuing ibrutinib treatment (rollover) and primary reasons for discontinuation of treatment for subjects who discontinued ibrutinib will be provided. Time on study will be summarized based on follow-up time of overall survival, and the median time on study will be estimated using Kaplan-Meier methodology. Information on ibrutinib treatment duration will be presented; the number and percentage of subjects with ibrutinib treatment over time will be summarized in 1-year intervals. Additionally, subject disposition will be summarized for subjects who will be included in each yearly interval.
Exposure to ibrutinib	Exposure will be summarized by treatment duration, cumulative dose received, and average daily dose during each yearly interval. The number of subjects continuing ibrutinib treatment in each yearly interval will be also summarized.
PFS2 assessed by investigator	 Duration from date of randomization to the date of the earliest of the following 3 types of events: PD per investigator response assessment after administration of the first subsequent anti-neoplastic therapy Death at any time on study from any cause Initiation of a second subsequent anti-neoplastic therapy The same methods used to analyze PFS will be used to analyze PFS2.
OS for crossover	OS after crossover to ibrutinib is defined from date of crossover to ibrutinib to the date of death due to any cause. Subjects who are alive or exited the study with unknown death status will be censored at the last date known to be alive. OS distribution is estimated by Kaplan-Meier method. Median OS and landmark estimates will be provided.

Interstitial lung	Interstitial lung disease events will be identified by ILD SMO-narrow. A summary of the prevalence
disease	of TEAEs and Grade 3 or higher TEAEs by yearly interval will be provided.
Clinical laboratory	The summaries of laboratory data will be presented by ibrutinib exposure intervals of 0-1 year, 1-2
test	years, 2-3 years, 3-4 years, 4-5 years, and >5 years (may be adjusted based on the actual data to
	ensure there are relatively enough subjects in the highest yearly interval) and overall.

Statistical Analysis Plan

A Randomized, Double-Blind, Placebo-Controlled, Phase 3 Study of Ibrutinib or Placebo in Combination with Rituximab in Subjects with Waldenström's Macroglobulinemia

РСҮС-1127-СА

13 October 2017

Version 2.0

Confidentiality Statement

The information in this document is considered privileged and confidential by Pharmacyclics LLC., and may not be disclosed to others except to the extent necessary to obtain Institutional Review Board approval and informed consent, or as required by Federal and State Laws. Persons to whom this information is disclosed must be informed that this information is privileged and confidential and that it should not be further disclosed.

Revision History

; structure and contents are re the major changes made:
f study and add a section for udy dosage and administration under the section for study ition in the section for blinding r to the protocol. ient reported outcomes (PRO). ndpoints. Add texts indicating ed at interim analysis and will e for subgroup analyses. gression-free survival and nse rate. nt of bone marrow, and lymph loratory endpoints. RO analysis and exploratory hypertension, interstitial lung eactions, rash, cardiac ion, infusion related reaction. ce rates.

TABLE OF CONTENTS

LIS	T OF ABBREVIATIONS	4
1.	INTRODUCTION	5
1.1.	Study Design	5
1.2.	Endpoints	6
1.3.	Statistical Hypotheses	6
1.4.	Sample Size Determination	7
1.5.	Planned Analyses	8
1.6.	Testing Procedure and Level of Significance	8
1.7.	Blinding and Randomization Methods	8
	1.7.1. Blinding Method	8
	1.7.2. Randomization Method	9
1.8.	Independent Data Monitoring Committee	9
2.	GENERAL ANALYSIS CONSIDERATION	9
2.1.	Analysis Sets	10
2.2.	Definition of Subgroups	10
2.3.	Handling of Missing Data for PRO Analysis	11
3.	SUBJECT INFORMATION	11
3.1.	Subject Disposition	11
3.2.	Demographics and Baseline Characteristics	12
3.3.	Prior and Concomitant Medications	12
3.4.	Extent of Exposure to Study Treatment	12

1. INTRODUCTION

This statistical analysis plan (SAP) lays out key elements including definitions and statistical methods for analysis of data in evaluation of efficacy and safety for the PCYC-1127-CA study. Analyses of pharmacokinetics data and biomarkers, and additional analyses of patient-reported outcomes (PROs) will be addressed in separate documents.

1.1. Study Design

This is a randomized, placebo-controlled, double-blind, Phase 3 study designed to evaluate whether treatment with ibrutinib in combination with rituximab will result in an improvement in progression-free survival (PFS) compared to placebo in combination with rituximab in subjects with WM (untreated and previously treated). In addition, an open-label ibrutinib substudy is included to further investigate the safety and efficacy of ibrutinib monotherapy in subjects with WM who are considered refractory to the last prior rituximab-containing therapy.

A total of 150 subjects were randomized in a 1:1 ratio to receive ibrutinib and rituximab (Treatment Arm A) or placebo and rituximab (Treatment Arm B). 31 subjects were enrolled in the open-label ibrutinib monotherapy substudy (Treatment Arm C). All subjects in Arm A and Arm B are to receive intravenous rituximab 375 mg/m² once weekly for 4 consecutive weeks, followed by a second 4-weekly rituximab course after a 3-month interval. In addition, all subjects in Arm A and Arm B, per randomization, are to receive oral study drug (420 mg ibrutinib or matching placebo), administered once daily and continuously until criteria for permanent discontinuation of study drug are met. All subjects in Arm C are to receive oral ibrutinib 420 mg, administered once daily and continuously until criteria for permanent discontinuation of study drug are met.

The study includes a Screening Phase, Treatment Phase and a Follow-Up Phase. All subjects are to be followed for disease progression until a PFS event occurs or until the data cutoff for final analysis.

Access to ibrutinib (cross-over) as next-line therapy for subjects with Independent Review Committee (IRC) confirmed disease progression and treated with placebo in combination with rituximab (Arm B) are provided as outlined in the protocol. Subjects who have symptomatic disease meeting criteria for requiring treatment may be eligible to receive ibrutinib as next-line therapy.

An IRC has been established to conduct response assessment and evaluate disease progression status centrally per the IRC charter.

1.2. Endpoints

Primary Endpoints

The primary endpoint is progression-free survival (PFS), as assessed by the IRC based on the modified Consensus Response Criteria from the VIth International Workshop for WM (NCCN 2014).

Secondary Endpoints

Secondary endpoints which will be tested include the following:

- Overall response rate (ORR) assessed by IRC (≥ partial response [PR]; according to the modified VIth IWWM [NCCN 2014] criteria)
- Time to next treatment (TTnT)
- Rate of sustained hemoglobin improvement
- Proportion of subjects with ≥ 3 points increase from baseline by Week 25 in fatigue experience score from the FACT-An 5 items assessing fatigue symptoms
- Overall survival (OS)

Safety Endpoints

Safety endpoints include adverse events, clinical laboratory tests, vital signs and eye-related symptoms.

Exploratory Endpoints

Exploratory endpoints include PFS by investigator, ORR by investigator, time to sustained hemoglobin improvement, duration of response (DOR), clinical response rate (CRR), medical resource utilization (MRU), IgM, hemoglobin (Hgb), lymph nodes and spleen measures, tumor involvement of bone marrow, EQ-5D-5L visual analog scale and utility score, FACT-An total score and subscale scores.

1.3. Statistical Hypotheses

The primary hypothesis of this study is that the experimental treatment ibrutinib + rituximab compared with placebo + rituximab will significantly improve PFS in subjects with WM.

The statistical hypotheses are as follows:

 H_0 : The PFS distributions of experimental treatment group, $S_I(t)$, and the control group, $S_C(t)$, are equal at all time points t:

```
S_{I}(t) = S_{C}(t), for all t > 0
```

versus

 H_1 : The PFS distributions of experimental treatment group, $S_1(t)$, are greater than the control group, $S_c(t)$, at at least one time point t:

 $S_{t}(t) > S_{c}(t)$, for some t > 0

These hypotheses will be tested using log-rank test.

1.4. Sample Size Determination

Treatment Arms A and B

This study was designed to evaluate the effect of treatment on PFS and was powered for this endpoint. The desired operating characteristics for the PFS endpoint were used to determine the study's total sample size and overall duration. The sample size and power calculations were based on a 2-sided log-rank test for PFS and the following considerations:

- 1:1 randomization ratio between 2 treatment arms
- Target hazard ratio of 0.5 with exponential distribution for PFS. Assuming the median PFS for the control arm (rituximab+placebo) was 15 months from randomization (this was based on available published data), a target hazard ratio of 0.5 corresponds to 2-fold increase in median PFS for the treatment arm (rituximab+ibrutinib) relative to the control (i.e., 30 months vs. 15 months, respectively)
- Minimum 80% power
- 2-sided overall significance level of 0.05
- One interim analysis at 70% information

The interim analysis was based on a group sequential design with Lan-DeMets spending function with O'Brien-Fleming boundary. Using the above assumptions and based on an estimated accrual rate of approximately 12 subjects per month, the study was to enroll approximately 150 subjects (about 75 subjects to each arm) to observe 71 events in approximately 27 months from the first subject randomized. Sample size was calculated using the software package, East 6 (Cytel Software Corp, Cambridge, MA).

Open-Label Substudy Treatment Arm C

The sample size for the substudy was not determined according to statistical calculation. 31 subjects were enrolled in this substudy.

1.5. Planned Analyses

A pre-specified interim analysis for the randomized treatment arms (Arms A and B) will be conducted after observing approximately 70% (~50) PFS events (progressive disease or death) based on IRC assessment. The final analysis of PFS will be conducted after approximately 71 PFS events are confirmed by the IRC for the randomized treatment arms (Arms A and B). The ibrutinib open-label monotherapy substudy (Arm C) will be summarized separately at the final analysis.

1.6. Testing Procedure and Level of Significance

Interim Analysis

In order to preserve the study wise 2-sided type I error rate of 0.05, the 2-sided significance level for PFS will be 0.015 at 50 PFS events for the interim analysis, based on O'Brien Fleming boundary. However, the alpha spending for PFS will be determined based on the actual information fraction using O'Brien-Fleming boundary at the time of the interim analysis.

If the primary endpoint achieves statistical significance, tests of secondary endpoints will be performed at the 2-sided significance level of 0.05 in a sequential hierarchical manner based on a closed testing procedure. The secondary endpoints will be ranked in sequence according to the hierarchical order specified below. OS will not be tested at interim analysis and will be tested at study closure.

- 1.) ORR
- 2.) TTnT
- 3.) Rate of sustained hemoglobin improvement
- 4.) Proportion of subjects with \geq 3 points increase from baseline by Week 25 in fatigue experience score
- 5.) OS

Final Analysis

The 2-sided significance level for the final analysis of primary endpoint (PFS) will be adjusted to account for interim alpha spending so the overall 2-sided significance level for the study will be preserved at 0.05. Tests of secondary endpoints will be performed using the same approach for the interim analysis.

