10.1. General Consideration

All analyses will be performed based on data up to the timepoint of clinical cutoff. Long-term follow-up data will be summarized separately when the entire study has completed. Statistical inferences will be based on a 2-sided Type I rate of 0.05 unless otherwise specified.

For the open-label substudy (Arm C), the efficacy and safety outcome of the substudy will be descriptively summarized and analyzed separately from the randomized treatment arms (Arm A and Arm B).

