10.8. Interim Analysis

An interim analysis for the randomized treatment arms (Arm A and Arm B) will be conducted at approximately 70% information, ~50 PFS events based on IRC assessment. The interim analysis will be performed by an independent statistical supporting group. PCYC will remain blinded to the results that are provided to the independent DMC at the interim analysis. In order to preserve the study wise two-sided type I error rate of 0.05, the two-sided significance level for PFS will be 0.015 at 50 PFS events, based on O'Brien Fleming boundary. However, the alpha spending for PFS will be determined based on the actual information fraction using O'Brien-Fleming boundary at the time of the interim analysis.

If the primary endpoint achieves statistical significance, tests of secondary endpoints will be performed at the two-sided significance level of 0.05 in a sequential hierarchical manner based on a closed testing procedure. All key secondary endpoints will be ranked in sequence according to a hierarchical order to be specified in the SAP. Further details regarding interim efficacy analysis will be described in the DMC charter and the SAP.

The ibrutinib monotherapy substudy (Arm C) will not be included in the interim analysis.

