10.9. Final Analysis

The final analysis will be conducted at approximately 71 PFS events, which are confirmed by the IRC for the randomized treatment arms (Arm A and Arm B). The two-sided significance level for the primary and all secondary endpoints will be adjusted to account for interim alpha spending so the overall two-sided significance level for the study will be preserved at 0.05. Tests of secondary endpoints will be performed using the same approach for the interim analysis. The ibrutinib monotherapy substudy (Arm C) will be analyzed separately at the final analysis.

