1. INTRODUCTION

This SAP is to describe the final analyses of data in evaluation of efficacy and safety of Study PCYC-1127-CA to support the Final CSR. The final analyses will be based on the final data extract. This SAP describes the additional analyses to the primary CSR SAP, dated 13 October 2017. All analyses that were performed previously for the primary CSR will follow the primary CSR SAP and will not be described again in this document. The additional analyses to support the Final CSR will be described in Section 2 (see summary in appendix Table 1).

2. ADDITIONAL ANALYSES

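### Protocol 10.9 adjusts the final level for PFS and all secondaries, SAP 1.6 for PFS only, and neither limits four secondaries to a single test, so 5% control is not guaranteed

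*SAP*

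**What the plan says.** **Interim.** SAP 1.6 puts PFS at 0.015 two-sided at 50 events. If PFS succeeds, "tests of secondary endpoints will be performed at the 2-sided significance level of 0.05 in a sequential hierarchical manner", in the order ORR, TTnT, sustained hemoglobin improvement, fatigue, OS. Protocol 10.8 gives the same level: "tests of secondary endpoints will be performed at the two-sided significance level of 0.05 in a sequential hierarchical manner".

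**Final.** Here the documents differ.

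- Protocol 10.9: "The two-sided significance level for the primary and all secondary endpoints will be adjusted to account for interim alpha spending".
- SAP 1.6: "The 2-sided significance level for the final analysis of primary endpoint (PFS) will be adjusted to account for interim alpha spending". For the secondaries: "Tests of secondary endpoints will be performed using the same approach for the interim analysis".

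**Timing.** Only OS has a timing rule: "OS will not be tested at interim analysis and will be tested at study closure". SAP 1.5 and Protocol 10.9 schedule the final analysis at about 71 events without making it depend on the interim result. Protocol 10.11 and SAP 1.8 leave stopping after an interim crossing to a possible DMC recommendation.

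**Long-term report.** The separate SAP for the Final CSR says: "All analyses that were performed previously for the primary CSR will follow the primary CSR SAP". Protocol 10.1 says: "Long-term follow-up data will be summarized separately when the entire study has completed".

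**Record of changes.** Protocol 10.6.2 leaves multiplicity details to the SAP. SAP section 5 names one major change, the added fatigue endpoint, and does not mention the narrower adjustment.

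**The concern.** Two things are unsettled.

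The first is the level that a secondary faces at the final analysis. Protocol 10.9 implies something below 0.05; SAP 1.6 implies 0.05.

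The second is how often a secondary may be tested. The fixed order and closed testing control error across endpoints within one analysis. They do not control it across two looks at the same endpoint. OS has a rule that prevents two looks; the four endpoints above it do not. If PFS crosses at the interim, a secondary misses 0.05 there and the trial continues to 71 events, SAP 1.6 as worded allows another test of that secondary at 0.05.

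At stake is whether a claim on one of these four endpoints carries the overall 5% that both documents promise.

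**Working it through.** **Inputs from the documents.** Overall two-sided 0.05, 71 final events, interim at 50, target hazard ratio (HR) 0.5, Lan-DeMets spending of O'Brien-Fleming type (Protocol 10.5, SAP 1.4 and 1.6).

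**Assumptions.** The documents give neither the information fraction of a secondary at the interim nor its correlation with PFS. I take the fraction as 50/71, with other values in step 4, and the correlation as 0, 0.5 and 0.9.

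**Step 1. The plan's own figure.** With t = 50/71 = 0.704 and √t = 0.839:

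- Interim level = 4[1 − Φ(2.2414/√t)] = 4[1 − Φ(2.671)] = 0.0151, which agrees with the stated 0.015. Boundary |z| = 2.429.
- The final boundary c solves 1 − P(|Z1| < 2.429, |Z2| < c) = 0.05 with correlation √t. This gives c = 2.001, a nominal level of 0.0454.

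**Step 2. A null secondary tested at both looks, ignoring the PFS gate.**

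- 0.05 then 0.05: 1 − P(|Z1| < 1.96, |Z2| < 1.96) = 7.5%. This is the ceiling at this fraction.
- 0.05 then 0.0454, which is Protocol 10.8 followed by Protocol 10.9: 7.2%. Restoring Protocol 10.9 alone therefore does not cure the problem.

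**Step 3. With the PFS gate.** The secondary is tested only once PFS has crossed. The PFS drift at the final look is |ln HR|·√71/2, which is 2.92 at HR 0.5 and 5.07 at HR 0.3. At HR 0.5, PFS crosses at the interim in 51% of trials and at either look in 83%. At HR 0.3 it crosses at the interim in 97%. Simulation with 3 million runs per cell gives, for correlation 0 / 0.5 / 0.9:

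| Rule | HR | Two-sided error, % | Favourable direction, % |
|---|---|---|---|
| Retest at 0.05 allowed | 0.5 | 5.4 / 4.8 / 3.8 | 2.7 / 3.6 / 3.8 |
| Retest at 0.05 allowed | 0.3 | 7.4 / 7.2 / 6.7 | 3.7 / 3.8 / 3.8 |
| One test, when PFS first crosses | 0.5 | 4.1 / 3.5 / 2.5 | 2.1 / 2.6 / 2.5 |
| One test, when PFS first crosses | 0.3 | 5.0 / 4.9 / 4.3 | 2.5 / 2.5 / 2.5 |

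Across all scenarios run, the single-test rule keeps two-sided error at or below 5.0%. Its highest favourable-direction value on the grid examined (HR 0.5-0.9, correlation 0.5-0.99) is about 3.5%, at HR 0.85 and correlation 0.99.

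**Step 4. Other information fractions, retest allowed, HR 0.5.**

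- Fraction 0.65: two-sided 5.6 / 4.9 / 3.9%, favourable 2.8 / 3.7 / 3.9%.
- Fraction 0.90: two-sided 4.9 / 4.2 / 3.3%, favourable 2.4 / 3.1 / 3.3%.
- An endpoint already complete at the interim has almost no excess. With 150 subjects at 12 per month, accrual ends at month 150/12 = 12.5 and the last Week 25 visit falls at about month 18.2. The design assumptions without dropout put the 50th event at about month 18.5, so fatigue is essentially complete by then. That model reaches 71 events at month 25.7 against the stated 27 or so, and Protocol 3.1 speaks of about 1.5 years of enrolment. If enrolment is that slow, some subjects may still be short of Week 25.

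**Step 5. The hierarchy.** Steps 3 and 4 apply to ORR, or to a lower endpoint only if the earlier ones almost surely succeed. For TTnT behind an ORR gate (assumed independent, 90% information at the interim, retest allowed), two-sided error is about 3.3-5.0% if ORR has 90% power and 3.0-4.4% if it has 80%.

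**The case against.** The strongest reply is that interim and final are alternative branches. A final PFS level adjusted for interim spending matters for a decision only if PFS was not already significant. On that reading each secondary is tested once, and two-sided error is 2.5-4.1% at HR 0.5. The reading is reasonable and may well be what was meant. It also removes any need to see Protocol 10.8 and 10.9 as contradicting each other, which a reader might infer. But the text does not say it, and the final analysis is scheduled unconditionally.

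The DMC charter, to which Protocol 10.8 refers for interim details, may contain a single-test rule. It was not available, so the point is confined to the protocol and SAP.

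On the documents' own two-sided criterion the excess at the design effect is small: only correlation near zero exceeds 5%. The 2.5% favourable-direction benchmark is half of the stated level; neither document states it. This stands, and it limits the size of the point.

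A reader might infer that the Final CSR adds a further formal test. The documents do not support that. Protocol 10.1 speaks of summarizing long-term data, which suggests description, although neither SAP says so.

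The silence of SAP section 5 is weak evidence, since that section claims to list only the major change.

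**Conclusion.** The difference between Protocol 10.9 and SAP 1.6 is plain in the text, and neither document states a single-test rule for ORR, TTnT, hemoglobin or fatigue. Following SAP 1.6 literally, 5% control is not guaranteed for these endpoints.

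For a null secondary whose earlier gates pass, the retest carries 3.8-5.4% two-sided error and 2.7-3.8% in the favourable direction at HR 0.5, resting on the assumed fraction of 50/71 and correlations from 0.9 to 0. A reader might take 7.5% as the trial's error rate. It is a ceiling, approached only if the drug works much better than planned (7.4% at HR 0.3, correlation 0) and only if a retest that no document prescribes is carried out. OS is unaffected, and fatigue almost so.

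This should be fixed because it touches a stated guarantee and the repair is wording only.

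**What to change.** **Preferred.** State in SAP 1.6 that each secondary except OS is tested once only, at two-sided 0.05 in the fixed order, at the analysis where PFS first crosses its boundary (interim or final). Any later repeat, including for the Final CSR, is descriptive. OS stays as planned. The cost is no second chance at the final analysis. Favourable-direction error can still slightly exceed 2.5% when a secondary is correlated with PFS: up to 2.6% at HR 0.5, and about 3.5% in the worst case examined.

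**If two looks are wanted.** Give each secondary except OS its own Lan-DeMets O'Brien-Fleming bounds, about 0.015 and 0.045 at 70% information. The information measure must be stated in advance. The documents give none for ORR or hemoglobin, and a count of randomized subjects would not serve because all 150 are already in (SAP 1.1). The interim bar rises from |z| 1.96 to 2.44. For a secondary with 90% fixed-design power at 70% information, interim power falls from 77% to 61%, while power over both looks is 89.6%.

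Under either choice, align Protocol 10.8 and 10.9 with SAP 1.6, check that the DMC charter agrees, and record the decision in SAP section 5. Sample size and data collection do not change.
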